5. Receipt of any polio (OPV or IPV) vaccine outside of study after enrolment (as per parent's report). Vaccine recipients who received polio vaccines outside of the study, including any polio vaccine administered in polio campaigns, would be excluded from further study procedures.
6. Temporary discontinuation may occur when there has been a temporary suspension of study activities. Study enrolment will be suspended from 12 weeks before the start of polio campaigns in the study areas to 6 weeks after the completion of polio campaigns in the study areas. This measure is to prevent potential interference from polio vaccine administered during polio campaigns in the study areas. If vaccine recipients receive vaccine during polio campaigns, they would be discontinued from further study procedures.

7. Unable to collect or obtain blood at enrolment (Clinic Visit at 6 Weeks of Age).
8. Allergic reaction to a prior dose of polio vaccine, or its contents.
9. Premature termination of the study.

Sibling

1. Vaccine recipient is discontinued from the study.
2. Withdrawal of consent for participation for any reason.
3. Receipt of any polio (OPV or IPV) vaccine after enrolment (as per parent's report). Siblings who receive polio vaccines during their participation in the study, including any polio vaccine administered in polio campaigns, would be excluded from further study procedures.

Description of Study Vaccines

Two polio vaccines will be used in the study: bOPV and nOPV2

1. Bivalent oral polio vaccine (bOPV)

- a. Manufacturer: Bio Farma
- b. Presentation: the vaccine will be available in multi-dose vials
- c. Formulation: Each dose (2 drops = 0.1 ml).
- d. Administration: one vaccine vial will be used per participant.
- e. Previous use at icddr,b: bOPV is part of the routine immunization schedule in Bangladesh.

2. Candidate 1 novel monovalent oral poliovirus vaccine type 2 (nOPV2)

- a. Manufacturer: Bio Farma

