Field workers will inform parents about the study and briefly explain the study procedures, including stool sampling from both the vaccine recipient and the sibling. If interested in participating, parents will be asked to visit the study clinic when the vaccine recipient is 6 weeks of age to obtain comprehensive information on the study and to complete enrolment procedures; both the vaccine recipient and sibling will need to be present at this visit. Parents will be provided transport costs for all study visits to/from the clinic.

The below description summarizes the study clinic and home visits over the course of the study. Vaccine recipients may additionally visit the study clinic for routine childhood vaccinations or for management of adverse events. Although non-study vaccines included in the routine immunization schedule in Bangladesh will be available and vaccination will be encouraged, parents will have the final decision to vaccinate their infant. Injectable non-polio, routine immunization vaccines will be administered at the recommended body site per the national guidelines of Government of Bangladesh. If a study visit involves collection of blood as well as administration of study vaccines, then blood collection will precede study vaccine administration. For Arm B, concomitant administration will be defined as nOPV2 provided first, followed by bOPV on the same day in rapid succession with a target of ≤ 5 minutes apart.

Enrolment visit – 6 weeks of age (acceptable range 42–48 days) [All arms; sibling must also be present at this clinic visit, but not subsequent clinic visits]

During this visit, the following procedures will be conducted:

1. The medical officer will confirm that the vaccine recipient and sibling are eligible to participate. If the vaccine recipient and sibling are eligible, all study procedures will be explained to the parents. The parents will be requested to provide informed consent; consent will be documented per study procedures.
2. The vaccine recipient will be assigned a participant identification number (PID) and to a study arm according to a pre-determined randomization scheme. Further details of the randomization scheme are described in the “Data Analysis” section.
3. Vaccination record of the sibling will be obtained and recorded by the medical officer.
4. Socio-demographic and clinical information will be recorded on the corresponding electronic case report form (eCRF).

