5. One blood specimen (1 ml) will be collected from the vaccine recipient by venipuncture.
6. The first dose of study vaccines will be administered to the vaccine recipient, as directed by study arm.
7. The vaccine recipient will be observed for 30 minutes to monitor for any adverse reactions from the blood collection or administration of study vaccines.
8. The vaccine recipient will receive the recommended routine childhood vaccinations, except polio vaccination. Routine polio vaccines will be replaced by the study vaccine.
9. Clinical information will be collected about the sibling. The sibling must be present at this visit so that he/she may be examined by a medical officer but does not need to be present for any subsequent clinic visits.
10. Schedule the household visit(s) and the next clinic visit.

Phone call or home Visit (24–48 hours after the first study vaccination) [All arms]

1. A study staff will contact the parents of the vaccine recipient to inquire and record any potential adverse events after the first study vaccination.
2. This phone call or visit will be conducted 24–48 hours after the first study vaccination visit.

Home Visit – 7 weeks of age [Arm A only]

Home Visit #1 (two days prior to 7 weeks of age)

1. The study field worker will visit the vaccine recipient's home and provide two plastic screw-cap stool containers to the mother. She will review the stool collection procedures with the mother, including sibling sampling.
2. The study field worker will complete the top portion of the study questionnaire.

Home Visit #2 (7 weeks of age)

1. Mother will collect stool specimens from the vaccine recipient and sibling. If possible, mother will collect fresh stool from each child's diaper or have the child defecate into a clean plastic pot. Mother will be asked to collect stool about the size of one adult thumb (8 grams). She will place the containers with the collected stool specimens immediately into the freezer (if available) or in a cool place in the home. The same procedures will be used for collecting stool specimens from the sibling. Mother will immediately notify the study field worker after each stool collection.

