5. The vaccine recipient will receive the recommended routine childhood vaccinations, except polio vaccination. Routine polio vaccines will be replaced by the study vaccine.
6. Schedule the next visit.

Study Clinic Visit – 14 weeks of age [All arms]

During this visit, the following procedures will be conducted:

1. The medical officer will complete the eCRF and examine the vaccine recipient.
2. One blood specimen (1 ml) will be collected by venipuncture.
3. Study vaccines will be administered, as directed by study arm.
4. The vaccine recipient will be observed for 30 minutes to monitor for any adverse reactions to the study vaccine.
5. The vaccine recipient will receive the recommended routine childhood vaccinations, except polio vaccination. Routine polio vaccines will be replaced by the study vaccine.
6. Schedule the next visit.

Study Clinic Visit – 18 weeks of age [All arms]

During this visit, the following procedures will be conducted:

1. The medical officer will complete the eCRF and examine the vaccine recipient.
2. One blood specimen (1 ml) will be collected by venipuncture.
3. Completion of study activities.
4. Vaccine recipients in Arms A and B will be given the first of three bOPV doses. Note: Arm B will be given three doses of bOPV to account for possible immunologic interference during co-administration of bOPV with nOPV2. All vaccine recipients will be given the first of two fIPV doses.

Timing of Evaluations

Entry/eligibility evaluations

- Entry evaluations will be completed at 6 weeks of age.
- Blood collection and study vaccine administration are planned during the study entry evaluation at 6 weeks of age. Blood will be collected before administration of any study vaccines. On the date of enrolment, study vaccines will be administered only if adequate blood specimen has been collected. If blood cannot be collected on the day of enrolment, study vaccine recipients will be discontinued from the study.
- The window for entry evaluation including collection of blood and administration of vaccine is 42–48 days of age.

Post-entry evaluations and follow-up

- After the first enrolment visit (6 weeks of age, range 42–48 days), the window for study visits is +/- 3 days.
- Blood will be collected before any study or EPI vaccines are administered.
- Stool collection from vaccine recipients and one sibling each will take place at 8 and 10 weeks of age for all Arms, and additionally at 7 weeks for Arm A only.

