who become seropositive ($\geq 1:8$) (seroconversion) or vaccine recipients who demonstrate at least a four-fold increase in titer (boosting). Baseline maternal antibody titer will be determined at 6 weeks of age and the estimated maternal antibody level at each blood collection will be calculated assuming an exponential decline with a half-life of 28 days. Vaccine recipients and siblings will be categorized for shedding poliovirus through results from multiple real-time PCR (rRT-PCR) assay designed to detect poliovirus. Household transmission will be defined as present if siblings test positive for nOPV2 vaccine virus at either 1, 2, or 4 weeks following the vaccine recipient's vaccination at 6 weeks of age. nOPV2 vaccine virus in stool specimens from vaccine recipients and siblings will be further characterized through high-resolution Illumina RNA sequencing. Intertypic vaccine-derived recombinants will be characterized in stool collected from study vaccine recipients and siblings.

Randomization

Vaccine recipients will be randomized to one of three arms using a block randomization scheme. The randomization algorithm will be generated by CDC staff and executed in REDCap. The randomization algorithm will not be known to study staff in icddr,b. Randomization assignment will be revealed after completing enrolment procedures, when study staff "click" on randomization button on the study tablets. Therefore, study staff enrolling and managing vaccine recipients will not have *a priori* knowledge of randomization scheme. As this is an open-label trial, the arm assignment of vaccine recipients will be known to study staff and the vaccine recipient's parents after randomization. Laboratory staff processing blood samples in Bangladesh will not have *a priori* knowledge of randomization scheme but will know the arm assignment after randomization. However, CDC laboratory staff testing for poliovirus antibody titers will remain blinded throughout the study.

Timeline of activities

Activities	Year 1 (months)					
	2	4	6	8	10	12
Protocol development/IRB approval, Staff training/site preparation						
Enrolment						
Start and completion of vaccination						
Follow up of vaccine recipients						
Lab testing						
Dissemination/Publications						

Data Analysis

General Issues

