5. Has the child had diarrhea in the last 24 hours (≥ 3 loose stools in 24 hours)? Yes / No
- 5a. If yes, specify: duration of diarrhea days
6. Is the child on any immunosuppressive medications? Yes / No 6a. If yes, specify _____

Physical Exam

7. Temperature: . °Celsius 8. Length #1: . cm 10. Weight #1: . kg
9. Length #2: . cm 11. Weight #2: . kg

Blood Collection

12. Blood sample collected? Yes / No 12a. If not, why? _____
13. Sufficient quantity (1 ml)? Yes / No 13a. If insufficient, why? _____
14. Time of collection (hh:mm) :

Study Group Allocation and Vaccine Administration

15. Specify which study group the child was allocated (*select the answer*):

- A: nOPV2 @ 6, 10, and 14 weeks
- B: nOPV2 + bOPV @ 6, 10, and 14 weeks
- C: bOPV @ 6, 10, and 14 weeks

Clinic Visit at 6 weeks of Age – Vaccine Recipient**Vaccine Administration***If Study Arm A or B*

16. nOPV2 administered? Yes / No 16a. If not, reason: _____

If administered: 16b. Time of vaccine administration (hh:mm): : 16c. Expiration (mmm/yy): / *If Study Arm B or C*

17. bOPV administered? Yes / No 17a. If not, reason: _____

If administered: 17b. Time of vaccine administration (hh:mm): : 17c. Expiration (mmm/yy): /

18. BCG administered? Yes / No 18a. If no and infant has yet to receive BCG, provide reason not given during today's visit: _____

If administered: 18b. Site of administration: Right arm / Left arm

19. Pentavalent administered? Yes / No 19a. If not, reason: _____

If administered: 19b. Dose: Penta1 / Penta2 / Penta3

19c. Site of administration: Right thigh / Left thigh

20. PCV administered? Yes / No 20a. If not, reason: _____

If administered: 20b. Dose: PCV1 / PCV2 / PCV3

20c. Site of administration: Right thigh / Left thigh

Observe for 30 minutes after vaccine administration:

21. Any symptoms? Yes / No

21a. If yes, specify (*complete Adverse Event Form, if required*): _____

Schedule next visit date (dd/MMM/yy):

Name and signature of medical officer: _____

Clinic Visit at 6 weeks of Age – SiblingDate of birth (dd/MMM/yy): / / Current age in years:

Sex: F / M

Eligibility criteria for sibling

1. Child is <10 years of age Yes / No
2. Child resides in the same household as the study vaccine recipient? Yes / No
3. Child will be available to participate in study activities for the next month? Yes / No
4. Child has NOT participated in a previous poliovirus vaccine clinical trial. Yes / No

Is this child eligible to be a sibling in the study? Yes / No

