Outcome (circle what applies): Ongoing / Resolved without sequela / Resolved with sequela / DeathDate when event resolved or death (dd/mm/yy): / /

Did this AE lead to discontinuation from the study or from future vaccinations? Yes / No

Adverse Event Form (cont.)**Study group allocation:** Specify which study group the child was allocated (*circle the answer*):

A: nOPV2 @ 6, 10, and 14 weeks
 B: nOPV2 + bOPV @ 6, 10, and 14 weeks
 C: bOPV @ 6, 10, and 14 weeks

Study vaccines administered:

Clinic visit	Study vaccines administered	Date (DD/MMM/YY)	Lot & batch number
6 weeks of age		____ / ____ / ____	
10 weeks of age		____ / ____ / ____	
14 weeks of age		____ / ____ / ____	

Routine immunization vaccines administered:

Clinic visit	Vaccines administered
At birth	
6 weeks of age	
10 weeks of age	
14 weeks of age	
18 weeks of age	
At any other age, specify age _____	

Signature of study investigator/s: _____

To be completed by the principal investigator

Is the event related to the study vaccine?

Unrelated Possibly related Probably related Definitely related

If unrelated to the vaccine, provide a reasonable explanation for the event (*e.g., other vaccine, blood collection, medical collection, etc.*) _____

_____Name and signature of PI: _____ Date / / /

Discontinuation Tracking Form – Vaccine Recipient

Date of the report (dd/mm/yy): / /

Date of study discontinuation (dd/mm/yy): / /

Note: This is the date the vaccine recipient is withdrawn from the study and may not be the same date as the report

Last clinic visit (circle one): 6 weeks / 10 weeks / 14 weeks

Date of last study clinic visit (dd/mm/yy): / /

Reasons (circle one of the choices listed below):

Discontinuation criteria as mentioned in study protocol:

1. Parent withdrew consent for participation (i.e., did not want child to participate any further).
2. The vaccine recipient received **polio vaccine** outside of the study. (**Complete protocol deviation form**)
3. Parent refused to allow collection of blood at 6 weeks of age. (**Complete protocol deviation form**)
4. Study staff were unable to collect blood at 6 weeks of age (**Complete protocol deviation form**)
5. Since enrolment, the vaccine recipient was diagnosed with a medical condition in which continued participation in the study posed a health risk (for example, immunodeficiency or bleeding disorder).
6. The vaccine recipient began taking immunosuppressive medications.

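### The protocol gives two orders for arm allocation and the required 6-week blood draw; under one of them infants can be excluded after the arm is known

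*Protocol*

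**What the plan says.** Three places in the protocol bear on the order.

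- **Study Procedures, enrolment visit at 6 weeks.** Step 1 is eligibility and consent. Step 2 reads "The vaccine recipient will be assigned a participant identification number (PID) and to a study arm according to a pre-determined randomization scheme". Steps 3 and 4 collect records and background data. Step 5 reads "One blood specimen (1 ml) will be collected from the vaccine recipient by venipuncture". Step 6 is the first study vaccine.
- **Appendix A, Clinic Visit at 6 weeks, Vaccine Recipient.** The blood items come first, starting with "12. Blood sample collected? Yes / No". Allocation follows: "15. Specify which study group the child was allocated".
- **Randomization.** "Randomization assignment will be revealed after completing enrolment procedures", by a click on the study tablet. The section does not say whether the blood draw is one of those procedures. It does say that staff and parents know the arm after randomisation.

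The consequence of having no blood is fixed elsewhere. Timing of Evaluations states: "If blood cannot be collected on the day of enrolment, study vaccine recipients will be discontinued from the study". Discontinuation criterion 7 for vaccine recipients says the same, and failure to obtain blood is not among the exclusion criteria. The vaccine-recipient Discontinuation Tracking Form has one reason for staff being unable to draw and another for refusal: "Parent refused to allow collection of blood at 6 weeks of age". Under Primary Analytical Approach, the set called intention-to-treat is limited to infants with a usable 6-week specimen.

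**The concern.** A baseline measurement without which an infant can be neither vaccinated nor analysed should be secured before the arm is allocated. If it comes afterwards, each failed or refused draw removes a randomised infant from the primary analysis, and in an open-label trial the parent or the staff member may know the arm when the draw is declined or abandoned.

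Arm-dependent refusal is possible here. The 6-week form lists reluctance about the blood draw as a reason for declining participation. The arms also differ visibly to parents: Arm A has an additional home visit and stool collection at 7 weeks, and receives no bOPV until 18 weeks. Each infant lost in this way also takes the sibling out, because sibling discontinuation follows from that of the vaccine recipient.

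**Working it through.** **1. The order, source by source**

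| Source | Allocation | Blood draw | Order |
|---|---|---|---|
| Enrolment-visit steps | step 2 | step 5 | arm first |
| 6-week form | item 15 | items 12–14 | blood first |
| Randomization section | after enrolment procedures | not mentioned | blood first only if the term covers the draw |

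The first two cannot both be followed. The third leans towards blood first but does not settle it.

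**2. The plan's own figures**

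Inputs from Sample Size: response 85%, margin 10%, power 90%, α 0.05 (sidedness not stated), 238 per arm, 10% attrition, target 265.

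- Uncorrected, one-sided 0.05: n = 2 × 0.85 × 0.15 × (1.645 + 1.282)² / 0.10² = 218.4.
- With continuity correction: (218.4/4) × [1 + √(1 + 4/(218.4 × 0.10))]² = 237.96, which gives 238.
- Attrition: 238/0.90 = 264.4, which gives 265.

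Both figures reproduce. The order of allocation and blood does not change them.

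**3. Effect on numbers and power if the arm comes first**

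The protocol gives no rate of failed draws, so x = 1% to 10% is assumed. Infants lost per arm = 265x. The later loss that still leaves 238 is 1 − 238/[265(1 − x)].

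| x | lost per arm | later loss still tolerable |
|---|---|---|
| 0 | 0 | 10.2% |
| 1% | 2.7 | 9.3% |
| 2% | 5.3 | 8.4% |
| 5% | 13.3 | 5.5% |
| 10% | 26.5 | 0.2% |

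With x = 5% and a separate 10% later loss, 265 × 0.95 × 0.90 = 226.6 infants remain per arm. Uncorrected power, Φ(0.10/√(2 × 0.85 × 0.15/n) − z), falls from 0.921 at n = 238 to 0.909 at one-sided 0.05. At one-sided 0.025 it falls from 0.863 to 0.846. Either way the change is under two points.

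**4. Possible bias if the arm comes first**

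Assume true response is 85% in both arms, and that a fraction x is excluded whose response, had they stayed, would have been q. The observed response is (0.85 − xq)/(1 − x). One arm excludes 2%; the other excludes more.

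| Extra exclusion | q = 0 | q = 0.5 | q = 1 |
|---|---|---|---|
| 1 point | +0.9 | +0.4 | −0.2 |
| 2 points | +1.8 | +0.7 | −0.3 |
| 5 points | +4.7 | +1.9 | −0.8 |

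Entries are shifts in the difference, in percentage points. For example, 0.85/0.96 − 0.85/0.98 = 0.8854 − 0.8673 = 0.0181. Equal exclusion of similar infants shifts nothing. If equal numbers are excluded but the infants differ (2% per arm, all non-responders in one and all responders in the other), the shift is 0.85/0.98 − 0.83/0.98 = 2.0 points.

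**The case against.** The strongest reply is that this is only a drafting slip. The form that staff complete at the visit already has blood before allocation, and the Randomization section defers the reveal. The step list is introduced as a summary and is not reliably chronological: it records the sibling's clinical information and examination at step 9, after vaccination, although step 1 already requires the sibling's eligibility, and one sibling exclusion rests on a physical examination. It also puts the infant's clinical information after allocation, where the form has it before. All of this stands, and it is why the step numbers alone cannot be read as proof that infants are randomised before the draw.

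A reader might also take criterion 7 and the discontinuation form as proof of loss after randomisation. They are not: a consented infant who has not yet been randomised could be recorded in the same way, and the discontinuation form has no field for the arm.

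Nothing in the protocol shows that refusal depends on the arm. Consent comes after all procedures have been explained, so parents have already accepted a blood draw in principle.

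What remains is that two explicit sequences conflict and no text says which governs. There is also a practical pull towards the step list. It issues the participant number together with the arm, the records section of the Data Safety Monitoring Plan says the number is provided after enrolment and randomisation, and laboratory specimens are to be identified by that number. Staff who need a number to label the tube have a reason to randomise first.

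**Conclusion.** The protocol contradicts itself on whether the arm is allocated before or after the required baseline draw. If the step list is followed, infants with failed or refused draws leave the primary analysis set after the arm is known. That is an avoidable possible source of bias in an open-label non-inferiority comparison.

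Its size cannot be derived from the document. The shifts shown rest on assumed exclusion rates and assumed responses among excluded infants. Large differential exclusion would matter against a 10-point margin; small or balanced exclusion of similar infants would not.

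Three stronger conclusions are not supported. The trial is not shown to randomise before blood, because the form says otherwise. The sample size is not undermined, because the power effect is minor. Drawing blood first would not bring baseline-specimen exclusions to zero, because haemolysed tubes are discarded later in the laboratory and the analysis set needs a specimen usable for serology.

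**What to change.** - **Enrolment-visit steps:** reorder to eligibility of both children, consent, adequate blood specimen, REDCap randomisation, then study vaccine. Tie the randomisation click to the form's items on blood collected and sufficient quantity.
- **Randomization section:** state that enrolment procedures include the blood draw.
- **Criterion 7 and the discontinuation form:** keep the record of failed and refused draws, but mark these infants and their siblings as not randomised. Criterion 7 need not be deleted.
- **Labelling:** provide a screening number or temporary label for the tube, linked to the participant number once it is issued.
- **Reporting:** give the number of randomised infants without a usable baseline specimen, including haemolysed tubes, by arm.

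The cost is wording, one line in the operating procedure and a label. The rule that study vaccine requires an enrolment specimen is unchanged. Some consented infants will not be randomised, so more must be approached: at an assumed 5% failure, 265/0.95 = 278.9, or about 279 consented for each 265 randomised.
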